14.1 DEFINITIONS

The categories of adverse events are shown in table 14.1-1. The definitions for each of these categories are given in the subsequent sections (see reference within the table).

Table 14.1-1: Categories of Adverse Event

	NOT DEVICE- RELATED	DEVICE- OR PROCEDURE-RELATED	
NON-SERIOUS	ADVERSE EVENT (AE) (SEE 14.1.1)	ADVERSE DEVICE EFFECT (ADE) (SEE 14.1.2)	
SERIOUS	SERIOUS ADVERSE EVENT (SAE) (SEE 14.1.3)	SERIOUS ADVERSE DEVICE EFFECT (SADE) (SEE 14.1.3)	
		ANTICIPATED	UNANTICIPATED
		ANTICIPATED SERIOUS ADVERSE DEVICE EFFECT (ASADE) (SEE 14.1.4)	UNANTICIPATED SERIOUS ADVERSE DEVICE EFFECT (USADE) (SEE 14.1.4)

14.1.1 Adverse Event

An AE is any untoward medical occurrence temporally associated with the use of an Investigational Product (IP)/Ancillary Product, whether or not considered causally related to that IP/Ancillary Product. AE is used both to refer to AEs which are non-serious non-IP or procedure-related and as an umbrella term referring to adverse events of all classifications.

14.1.2 Adverse Device Effect

An ADE is an adverse event that, in the opinion of the Investigator, is related to the IP or the procedure.

Not Related - An AE is considered to be not related to the use of an IP or the procedure when the effect is DEFINITELY UNRELATED or UNLIKELY to have any relationship to the use of the IP or the procedure;

CONFIDENTIAL AND PROPRIETARY

This document contains information that is confidential and proprietary to Smith & Nephew PLC and Smith & Nephew, Inc. and is intended for use only by Smith & Nephew and its manufacturer. It shall not be reproduced or copied in whole or in part, nor shall the contents be disclosed by any means without prior written permission from Smith & Nephew, nor shall anyone make any use of it that is contrary to the expressed or implied wishes of Smith & Nephew.

Study Protocol—Device	
Safety and Performance of Q-Fix™ All-Suture Anchor System	Number: 17-5010-11
	Version: 2.0 05SEP2019
	Page: Page 33 of 62

Related – An AE is considered to be related to the use of an IP or the procedure when there is a POSSIBLE, PROBABLE, or DEFINITE relationship between the AE and the use of the IP or the procedure.

An ADE is further categorized depending on whether the criteria in section 14.1.3 and 14.1.4 are met.

14.1.3 Serious Adverse Events and Serious Adverse Device Effects

An AE or ADE is considered a SAE or SADE if, in the view of either the Investigator or the Sponsor, it:

- Results in death.
- Is life-threatening (*NOTE: The term “life-threatening” in the definition of “serious” refers to an event/reaction in which the subject was at risk of death at the time of the event/reaction; it does not refer to an event/ reaction which hypothetically might have caused death if it were more severe*).
- Requires in subject hospitalization or results in prolongation of existing hospitalization.
- Results in persistent or significant incapacity or substantial disruption of the ability to conduct normal life functions.
- Is a congenital anomaly/birth defect.
- Is a medically important event or reaction.

Medical and scientific judgment should be exercised in deciding whether other situations should be considered serious such as important medical events that might not be immediately life-threatening or result in death or hospitalization but might jeopardize the subject or might require intervention to prevent one of the other outcomes listed in the definition above. Examples of such events are intensive treatment in an emergency room or at home for allergic bronchospasm, blood dyscrasias, or convulsions that do not result in hospitalization; or development of drug dependency or drug abuse.

14.1.4 Anticipated/Unanticipated Serious Adverse Device Effect

CONFIDENTIAL AND PROPRIETARY

This document contains information that is confidential and proprietary to Smith & Nephew PLC and Smith & Nephew, Inc. and is intended for use only by Smith & Nephew and its manufacturer. It shall not be reproduced or copied in whole or in part, nor shall the contents be disclosed by any means without prior written permission from Smith & Nephew, nor shall anyone make any use of it that is contrary to the expressed or implied wishes of Smith & Nephew.

Study Protocol—Device	
Safety and Performance of Q-Fix™ All-Suture Anchor System	Number: 17-5010-11
	Version: 2.0 05SEP2019
	Page: Page 34 of 62

An USADE is a serious ADE that meets any of the above definitions but is also considered, by the Investigator, to be caused by or related to the IP, not previously identified in nature, severity or degree in the IFU.

An Anticipated Serious Adverse Device Effect (ASADE) is a serious ADE that does not meet the criteria for a USADE.

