#### **CONFIDENTIAL AND PROPRIETARY**

This document contains information that is confidential and proprietary to Smith & Nephew PLC and Smith & Nephew, Inc. and is intended for use only by Smith & Nephew and its manufacturer. It shall not be reproduced or copied in whole or in part, nor shall the contents be disclosed by any means without prior written permission from Smith & Nephew, nor shall anyone make any use of it that is contrary to the expressed or implied wishes of Smith & Nephew.

Statistical Analysis Plan	
Safety and Performance of Q-Fix ® All-Suture Anchor System	Number: 17-5010-11
	Version: 2.0, 23-Oct-2019
	Page: 14 of 20

End Date for SAE will be based on the AE Stop Date or Death Date as found in the Related AE.

When there is a Follow-up AE, the end date will come from the AE Stop Date or Death Date on the latest or highest numbered Follow-up AE.

Also, a check will be performed for all bilateral knee subjects to remove from the AE summaries the double entries referencing the same Adverse Event for a single implant twice. Where an AE CRF is filled out regarding the contralateral knee after an AE has already been reported for the ipsilateral knee.

An ADE is defined as an Adverse Event that is Possibly or Probably Related to Device or Procedure.

The Expectation variable on the AE CRF is only to be filled out for Serious ADEs.

All Adverse Events will be assessed by the Investigator to determine relatedness and severity. The AEMB may subsequently classify events into SAEs, ADEs, SADEs, UADEs, USADEs etc. All safety Tables will presented based on the Investigator's and/or AEMB classifications.

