#### Number of Adverse Events by Classification

ADVERSE EVENTS	NON DEVICE-RELATED	DEVICE-RELATED	
NON-SERIOUS	ADVERSE EVENT (AE)	ADVERSE DEVICE EFFECT (ADE)	
	<device>	<device>	
	<#> x%	<#> x%	
SERIOUS	SERIOUS ADVERSE EVENT (SAE)	SERIOUS ADVERSE DEVICE EFFECT	
		ANTICIPATED	UNANTICIPATED
		ANTICIPATED SERIOUS ADVERSE DEVICE EFFECT (ASADE)	UNANTICIPATED SERIOUS ADVERSE DEVICE EFFECT (USADE)
	<device>	<device>	<device>
	<#> x%	<#> x%	<#> x%

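### A serious procedure-only event that is not in the IFU cannot be counted as unanticipated, because protocol 14.1.4 ties that class to the device and defines the anticipated class as the remainder

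*Protocol*

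**What the plan says.** Four definitions and two sets of tables bear on this.

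- Protocol 14.1.2 sets the scope of an adverse device effect: "An ADE is an adverse event that, in the opinion of the Investigator, is related to the IP or the procedure".
- Protocol 14.1.3 adds seriousness without changing that scope: "An AE or ADE is considered a SAE or SADE if, in the view of either the Investigator or the Sponsor, it" meets one of the listed criteria.
- Protocol 14.1.4 defines a USADE as a serious ADE that must in addition be "considered, by the Investigator, to be caused by or related to the IP, not previously identified in nature, severity or degree in the IFU". The procedure is not named.
- Protocol 14.1.4 defines the anticipated class only by exclusion: "An Anticipated Serious Adverse Device Effect (ASADE) is a serious ADE that does not meet the criteria for a USADE".

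Protocol Table 14.1-1 heads its related column "DEVICE- OR PROCEDURE-RELATED" and divides the serious events in it into anticipated and unanticipated.

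SAP 7.4.4 keeps the wide scope: "An ADE is defined as an Adverse Event that is Possibly or Probably Related to Device or Procedure". It gives no USADE definition of its own. The SAP 7.9.4 tables, one counting events and one counting patients, have separate cells for anticipated and unanticipated serious device effects. Their columns, however, are headed device-related and non device-related, with no mention of the procedure.

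**The concern.** The class called unanticipated has a narrower relatedness test than the parent class it is taken from. The class called anticipated takes whatever is left and has no test of its own. An event can therefore be called anticipated without anyone having found it in the IFU.

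This is a post-market study whose stated purpose is to address gaps in the clinical data on the device. It covers open and arthroscopic surgery and allows data on uses beyond the listed indications. Serious procedure-related events are a foreseeable class in such a study. If one occurs that the IFU does not describe, the SAP tables should not imply that it was expected, and their unanticipated cell should not omit it merely because of how the definition is worded.

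**Working it through.** The plan gives no figure to reproduce. The check applies the protocol definitions to every kind of serious ADE: three kinds of relatedness crossed with two IFU states, so 3 × 2 = 6 cases.

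| Related to | Identified in IFU? | Serious ADE (14.1.2, 14.1.3)? | Meets USADE test (14.1.4)? | Label |
|---|---|---|---|---|
| Device only | Yes | Yes | No, identified | Anticipated |
| Device only | No | Yes | Yes | Unanticipated |
| Both | Yes | Yes | No, identified | Anticipated |
| Both | No | Yes | Yes | Unanticipated |
| Procedure only | Yes | Yes | No, identified and not related to the IP | Anticipated |
| Procedure only | No | Yes | No, not related to the IP | Anticipated, by remainder |

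Five labels agree with the IFU status; the last does not. Of the three unlisted cases, two reach the unanticipated class. With the procedure included in the USADE test, all three would, and the anticipated class would hold only the three listed cases.

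**Can IP be read to include the procedure?** No. Protocol 14.1.2 names the two separately wherever it means both. Sections 14.2 and 14.3.1 also keep them apart, and the SAP 7.9.4 listing has one field for relationship to the device and another for relationship to the procedure.

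**Where does the event land in the SAP tables?** There are two readings.

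1. By the ADE definition in SAP 7.4.4, it is a serious ADE. With no separate USADE definition in the SAP, protocol 14.1.4 sends it to the anticipated cell.
2. By the column heading in SAP 7.9.4, it is not device-related, so it goes to the SAE cell.

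The documents do not decide between them. Under either reading the event is absent from the unanticipated cell.

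**Size.** Neither document gives a rate for such events, and the IFU is not reproduced, so no expected count can be computed. Each affected event is one fewer in the unanticipated cell. As a share of subjects, one affected subject is:

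- at the planned minimum, 1/90 = 1.1%
- at the planned maximum, 1/450 = 0.2%

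**The case against.** The best case for leaving the text alone is that little depends on this label.

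- Under protocol 14.2, ADEs and SAEs go to the sponsor within 24 hours, and all are reviewed by a medically qualified person for expedited reporting, whether labelled anticipated or not.
- SAP 7.4.4 says the AEMB may reclassify events, and that the tables rest on the investigator's and/or the AEMB's classification.
- The SAP 7.9.4 listing shows, for each event, relationship to device, relationship to procedure, seriousness and expectation. A careful reader could find the event there.
- USADE is not a named endpoint, and protocol 12.4 does not include anticipation among the breakdowns of its adverse event summaries.

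Most of this stands. It confines the problem to the classification tables. It does not remove it: AEMB reclassification is optional and has no different definition to work from, and a listing does not correct a summary cell. The listing helps only if the expectation field is completed, which SAP 7.4.4 requires for serious ADEs alone. It also assumes the field is answered against the IFU, and the documents do not say so.

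Three stronger readings are tempting and not supported.

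- A reader might infer that such an event is certain to be reported as anticipated. The SAP column headings leave open that it goes to the non-device SAE cell, where it carries no such label.
- A reader might infer that safety reporting is weakened. Protocol 14.2 shows otherwise.
- A reader might infer that the unanticipated count will be materially understated. The documents give no basis for expecting even one such event.

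**Conclusion.** The concern holds as an inconsistency of scope between definitions. Protocol 14.1.2 and Table 14.1-1 admit procedure-related events to the serious device effects, while 14.1.4 excludes procedure-only events from the unanticipated class and assigns them to the anticipated class with no IFU test. One of six cases gets a label that contradicts its IFU status. The SAP carries the inconsistency forward and adds a second through its column headings.

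The consequence is limited to classification and tabulation. Its size is unknown and may be zero; one affected subject is 0.2% to 1.1% of those enrolled across the planned range of 450 down to 90. The conclusion rests on a literal reading of 14.1.4 and assumes that the AEMB, if it reclassifies, uses the protocol's definitions, since the SAP supplies no others.

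**What to change.** 1. In protocol 14.1.4, define the anticipated class positively: a serious ADE whose nature, severity and degree are all identified in the IFU.
2. Use one relatedness scope for ADE, SADE and USADE in protocol 14.1.2, Table 14.1-1 and 14.1.4, and in SAP 7.4.4 and 7.9.4. Two routes are consistent: extend the USADE test to the procedure, or keep it tied to the device and give procedure-only serious events their own cell, split by expectation. The documents do not favour either; the sponsor should choose and state the choice.
3. Make the column headings of both SAP 7.9.4 tables match that scope.
4. State that the expectation field is judged against the IFU.

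Printing device-related and procedure-only events on separate lines beyond this is a matter of presentation.

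The cost is wording in both documents. The expectation field and the two relatedness fields are already collected, so no new data item should be needed. Protocol section 12 has the SAP finalised before database lock and lets it account for changes to the planned analyses. If a protocol amendment seems disproportionate, a rule stated in SAP 7.4.4 and 7.9.4 would correct the tables, though 14.1.4 would still read as it does. The downside is that the unanticipated count may rise.

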14.1.5 Severity

The severity of every AE will be assessed by the Investigator or medically qualified site staff to whom the responsibility has been delegated and documented on the delegation of authority log. AE should be classified as mild, moderate, or severe, regardless of whether or not the AE are considered to be serious or non-serious. The classification should be based on the following definitions:

Mild - An event is mild if the subject is aware of, but can easily tolerate the sign or symptom;

Moderate - An event is moderate if the sign or symptom results in discomfort significant enough to cause interference with the subject’s usual activities;

Severe - An event is severe if the sign or symptom is incapacitating and results in the subject’s inability to work or engage in their usual activities.

14.1.6 Device Deficiency

A Device Deficiency (DevD) is an inadequacy of a medical device with respect to its identity, quality, durability, reliability, safety or performance. DevD includes malfunctions, use errors and inadequate labelling.

14.2 REPORTING PROCEDURES

AEs of any kind and DevDs will be recorded in the applicable CRF and source notes. The Investigator will evaluate all AEs for relationship to the device and procedure, if applicable, seriousness, and severity.

CONFIDENTIAL AND PROPRIETARY

This document contains information that is confidential and proprietary to Smith & Nephew PLC and Smith & Nephew, Inc. and is intended for use only by Smith & Nephew and its manufacturer. It shall not be reproduced or copied in whole or in part, nor shall the contents be disclosed by any means without prior written permission from Smith & Nephew, nor shall anyone make any use of it that is contrary to the expressed or implied wishes of Smith & Nephew.

Study Protocol—Device	
Safety and Performance of Q-Fix™ All-Suture Anchor System	Number: 17-5010-11
	Version: 2.0 05SEP2019
	Page: Page 35 of 62

ADEs, SAEs, and DevDs will be submitted/entered into the CRF and reported to the Sponsor within 24 hours of the Investigator being informed about the event (Figure 14.2-1). For ADEs and DevDs, details of the product/procedure related to the event will be included and where applicable, pictures taken of the device. The deficient product should be retained for return to the sponsor unless it is contaminated (e.g. used dressings must not be retained). Updates to submitted information will be recorded in the CRF within 24 hours of the information being available to the Investigator.

[figure not shown]
All SAEs and ADEs will be reviewed by a medically qualified person appointed by the Sponsor to determine which, if any, meet criteria for expedited reporting to the regulatory authorities. The Investigator will inform the IRB of AEs according to the IRB requirements.

Depending on the nature of the AE, the Sponsor may request copies of the subject’s medical records, imaging, operative notes, as well as results of any relevant laboratory tests performed or other documentation related to the AE. If the subject was hospitalized, a copy of the discharge summary may be requested by the Sponsor and should be forwarded as soon as it becomes available. In certain cases, the Sponsor also may request a letter from the Investigator that summarizes the events related to the case.

CONFIDENTIAL AND PROPRIETARY

This document contains information that is confidential and proprietary to Smith & Nephew PLC and Smith & Nephew, Inc. and is intended for use only by Smith & Nephew and its manufacturer. It shall not be reproduced or copied in whole or in part, nor shall the contents be disclosed by any means without prior written permission from Smith & Nephew, nor shall anyone make any use of it that is contrary to the expressed or implied wishes of Smith & Nephew.

Figure 14.2-1: Evaluation and Reporting of AE and DevD

Reference the Investigator Site File Sponsor Contact Information Sheet to report SAEs, unanticipated ADEs and SADEs, anticipated SADEs, and DevDs.

CONFIDENTIAL AND PROPRIETARY

This document contains information that is confidential and proprietary to Smith & Nephew PLC and Smith & Nephew, Inc. and is intended for use only by Smith & Nephew and its manufacturer. It shall not be reproduced or copied in whole or in part, nor shall the contents be disclosed by any means without prior written permission from Smith & Nephew, nor shall anyone make any use of it that is contrary to the expressed or implied wishes of Smith & Nephew.

Study Protocol—Device	
Safety and Performance of Q-Fix™ All-Suture Anchor System	Number: 17-5010-11
	Version: 2.0 05SEP2019
	Page: Page 37 of 62

14.3 FOLLOW-UP OF SUBJECTS WITH ADVERSE EVENTS

For subjects who are experiencing an ongoing unresolved AE at the time of their study completion or early discontinuation from the study, it is recommended that the Investigator schedule an appropriate follow-up visit in order to determine the outcome of the event.

Any additional data must be documented and available to the Sponsor who will determine whether the data need to be documented within the CRF/Clinical Study Report.

14.3.1 Ongoing Adverse Events at Study Discontinuation

Adverse events which are **related** to a study procedure or IP and are ongoing at end of subject's participation: The event should be followed until it is either resolved or until the event has become chronic and is not expected to further improve based on Investigator's review of the event.

Adverse events which are **not related** to a study procedure or IP and are ongoing at end of subject's participation should be followed for 30 days after discontinuation or if the AE is resolved, whichever is sooner.

At the time of data analysis (e.g. interim or final), an evaluation of ongoing events should take place and be listed as ongoing in the safety table.

15. INVESTIGATOR OBLIGATIONS

The Principal Investigator (PI) will comply with the commitments outlined in the in the Statement of Investigator and with GCP, and all applicable regulatory requirements as outlined in Appendix 23.2 of this protocol.

CONFIDENTIAL AND PROPRIETARY

This document contains information that is confidential and proprietary to Smith & Nephew PLC and Smith & Nephew, Inc. and is intended for use only by Smith & Nephew and its manufacturer. It shall not be reproduced or copied in whole or in part, nor shall the contents be disclosed by any means without prior written permission from Smith & Nephew, nor shall anyone make any use of it that is contrary to the expressed or implied wishes of Smith & Nephew.

Study Protocol—Device	
Safety and Performance of Q-Fix™ All-Suture Anchor System	Number: 17-5010-11
	Version: 2.0 05SEP2019
	Page: Page 38 of 62

16. SPONSOR AND MONITOR RESPONSIBILITIES

The Sponsor will designate a monitor to conduct the appropriate site visits at the appropriate intervals. The clinical investigation will be monitored to ensure that: the rights and wellbeing of the subjects are protected; the reported data are accurate, complete, and verifiable from the source documents; and the study is conducted in compliance with the currently approved protocol, with GCP regulations, and with applicable regulatory requirements.

Detailed monitoring requirements will be documented within the Clinical Monitoring Plan for this study.

16.1 SITE QUALIFICATION VISIT

A site qualification visit may be performed by the Sponsor prior to the execution of a clinical agreement to ensure that all Investigators have the appropriate training, staff, facilities, and resources to adequately conduct the study.

16.2 SITE INITIATION VISIT

A site initiation visit to provide training on the specifics of the study, site obligations and expectations of study conduct will be performed by the Sponsor or qualified person designated by the Sponsor following the execution of the Clinical Trial Agreement (CTA) and documented IRB approval.

16.3 SPONSOR AUDITS AND REGULATORY INSPECTION

Quality Assurance auditors, whether an employee of the Sponsor or its designee, may evaluate study conduct at the study sites. These parties must have access to any and all study reports and source documentation, regardless of location and format.

CONFIDENTIAL AND PROPRIETARY

This document contains information that is confidential and proprietary to Smith & Nephew PLC and Smith & Nephew, Inc. and is intended for use only by Smith & Nephew and its manufacturer. It shall not be reproduced or copied in whole or in part, nor shall the contents be disclosed by any means without prior written permission from Smith & Nephew, nor shall anyone make any use of it that is contrary to the expressed or implied wishes of Smith & Nephew.

Study Protocol—Device	
Safety and Performance of Q-Fix™ All-Suture Anchor System	Number: 17-5010-11
	Version: 2.0 05SEP2019
	Page: Page 39 of 62

16.4 CLOSE-OUT VISIT

A study close-out visit will be performed by the Sponsor or designee to retrieve and account for all remaining clinical data and to resolve outstanding queries. During study close-out, the monitor will review investigator files to ensure required documents and records are on file, confirm the disposition of any other ancillary items used for the study, and review regulatory requirements regarding records retention and IRB/IEC reporting requirements.

